3.2.2. Maximum Dose

An upper limit of 35 mg per day is supported by the nonclinical data and human PK data, specifically by exposure at the 1/10th of the NOEL of 2.75 mg/kg established in the 14-day dog EEG study, however this will be guided by emerging safety and PK data. Dose escalation will stop at any time if unacceptable safety findings are identified or if the maximum concentration (C_{max}) or area under the curve (AUC) exceeds or is likely to exceed 1/10th of the exposure associated with the NOEL of 2.75 mg/kg seen in the 14-day dog EEG study (84.9 ng/mL or 82.7

h×ng/mL for KNX100 and 26.5 ng/mL and 45.7 hr × ng/mL for KNX100A, respectively). In this case, the CRC may stop the study, or modify the dose downwards in subsequent cohorts.

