
Planned Number of Patients: Approximately 64 healthy subjects will be randomized for study participation. The total number of subjects will depend on the number of dose levels assessed during dose-escalation to determine the Recommended Phase 2 dose (RP2D) of KNX100.
 
Randomization will be controlled either via a list or Interactive Web Response System.
	

Diagnosis and Main Criteria for Inclusion: This study will evaluate healthy volunteers (male and female) who are between 18 and 55 years of age (inclusive) with a body mass index (BMI) of 18-32 (inclusive). Subjects must be willing to comply with study requirements and must agree to abstain from consuming alcohol or using recreational drugs. Subjects with specific underlying conditions (e.g., mental illness, human immunodeficiency virus (HIV), hepatitis, cardiovascular disease) or any medical history that would jeopardize their safety cannot participate. Additionally, subjects with clinically significant electrocardiogram (ECG),
	

electroencephalogram (EEG), physical examination, or laboratory findings will not be enrolled. Female subjects of childbearing potential must be willing and able to use defined methods of contraception throughout the study and for 30 days after the final follow-up visit.

Test Product; Dose; and Mode of Administration: KNX100 will be provided in capsule form as 5, 25 or 100 mg capsules for oral administration. Study drug will be encapsulated in hydroxypropyl methylcellulose (HPMC) dark green opaque size 0 capsules and packaged in 100 mL high density polyethylene (HDPE) bottles with polypropylene twist-off closures. Dosing will be based on the assigned treatment group. This study will evaluate doses of KNX100 starting with a single ascending dose (Part A, SAD) of 5 mg, increasing up to a maximum of 50 mg and a multiple ascending dose (Part B, MAD) starting at 10 mg and increasing up to 35 mg per dose, as tolerated. Individual doses will be dispensed by unblinded site pharmacy staff. Dose escalation will progress upon CRC approval. Subjects will take the study drug in the morning after an overnight fast. For subjects enrolled into MAD Cohort 3, subjects will take study drug in the morning after an overnight fast and again, approximately 8 hours after the first dose following a 2-hour fast.

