Dose: This study employs a SAD followed by a MAD design. Part A Cohort 1 will initially evaluate a low dose of KNX100 (5 mg). For the following cohorts (2-4), the KNX100 dose will be increased as agreed by the CRC up to a maximum of 50 mg of KNX100 (Table 3) or to the maximum exposure level defined in Section 6.20.1, whichever occurs first. In Part B (MAD), dosing will initially evaluate a low dose of 10 mg, followed by a high dose to be selected based on safety, tolerability and exposure data generated in Part A. Cohort 3 of Part B will evaluate twice daily (b.i.d) dosing. The dose will be selected based on PK data from the preceding cohort. KNX100 and placebo will be encapsulated in identical size 0 capsules to ensure blinding of study treatment. Additionally, subjects assigned to receive placebo will have the same number of capsules as subjects receiving KNX100. Predefined stopping rules are provided to ensure the safety of all study subjects are defined in Section 6.20.

Control: A matching placebo control will be administered to evaluate treatment-related effects.

Population: KNX100 has not been previously administered to humans; therefore, its effects in humans are as yet unknown. A healthy volunteer population with carefully considered inclusion/exclusion criteria will avoid the potential for interaction of KNX100 with any underlying disease state or concomitant medication that it may be necessary for subjects to take, while ensuring that subjects are fit and well enough for participation in the study. Females of child-bearing potential will have to undergo a pregnancy test prior to enrollment.

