5.2. Treatments Administered

Both KNX100 and placebo will be administered orally based on the assigned treatment group (refer to [Section 5.3](#)). For each cohort, a total of 8 subjects will be dosed (6 with KNX100 and 2 with placebo).

Part A will evaluate doses of KNX100 starting with 5 mg and increasing up to a maximum of 50 mg per day ([Table 3](#)). Doses post the 5 mg dose will be decided by the CRC upon review of all available data.

Part B will evaluate a low- (10 mg), and high-dose, based on the doses evaluated in Part A and the safety, tolerability, and PK of doses in the previous cohorts, administered for 7 consecutive days ([Table 4](#)). Part B (Cohort 3) will evaluate twice daily dosing of a single dose, selected based on the safety, tolerability, and PK of doses in the previous cohorts, administered for 7 consecutive days ([Table 4](#)).

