5.3.2. Part A Dosing

Study drug will be administered once on Day 1. Part A dosing will commence with 2 sentinel subjects prior to dosing the remainder of each cohort (refer to [Section 5.3.1](#)).

Study drug will be administered in the morning together with a glass of tap water under a fasted state, i.e., after an overnight fast of at least 10 hours and no food is allowed for at least 2 hours after drug administration. Please refer to [Section 5.10.3](#) for information related to fluid and food restrictions both pre- and postdose.

[Table 3](#) provides the planned dose-escalation schedule. Of note, dose escalations will not exceed dose-doubling in principle.

Table 3 Planned Dose-Escalation Schedule (SAD Part A)

Cohort	Oral Daily Dose (mg/day) ¹		Total Number of Capsules (Number - Strength) ¹	
	KNX100	Placebo	KNX100	Placebo ²
1	5	0	1 capsule (1 × 5 mg)	1 capsule (1 × 0 mg)
2	15	0	3 capsules (3 × 5 mg)	3 capsules (3 × 0 mg)
3	25	0	25 mg: 1 capsule (1 × 25 mg)	25 mg: 1 capsule (1 × 0 mg)
4	50	0	50 mg: 2 capsules (2 × 25 mg)	50 mg: 2 capsules (2 × 0 mg)

Abbreviations: PK = pharmacokinetics.

¹ All dose levels beyond Cohort 1 may change based on emerging safety and PK data.

² An equivalent number of capsules will be administered to subjects receiving placebo.

*Additional cohorts may be added as required, based on safety profile and CRC authorization.

Dose escalation and de-escalation will follow the processes outlined in [Section 5.3.4](#).

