5.3.3. Part B Dosing

In Cohorts 1 and 2, study drug will be administered once daily for 7 days at approximately the same time each day \pm 30 minutes. In Cohort 3, study drug will be administered twice daily, approximately 8 hours (\pm 30 minutes) apart for 7 days. Doses will be administered:

- Morning (e.g., at 11:00 am) at approximately the same time (\pm 30 minutes) each day
- Afternoon/ Evening (e.g., at 7:00 pm) at approximately the same time (\pm 30 minutes) each day

The first dose of study drug will be administered together with a glass of tap water under a fasted state i.e., after an overnight fast of at least 10 hours. For MAD Cohort 3, the second dose of study drug will be administered together with a glass of tap water under a fasted state i.e., after fasting for at least 2 hours prior to dose administration. For all cohorts, no food is allowed for at least 2 hours after drug administration. Please refer to [Section 5.10.3](#) for information related to fluid and food restrictions both pre- and postdose.

[Table 4](#) provides the planned dose-escalation schedule for Part B (MAD). Up to 2 dose strengths ranging from as low as 10 mg and up to the clinical exposure cap will be selected based on the tolerability and pharmacokinetics of the previous dose.

Table 4 Planned Dose-Escalation Schedule (MAD Part B)

Cohort	Oral Daily Dose (mg/day) ¹		Total Number of Capsules/Day (Number - Strength) ¹	
	KNX100	Placebo	KNX100	Placebo ²
1	10 (Low)	0	2 capsules (2 × 5 mg)	2 capsules (2 × 0 mg)
2	30 (High)	0	2 capsules (1 × 5 mg, 1 × 25 mg)	2 capsules (2 × 0 mg)
3	30 (bid) ³	0	2 capsules (1 × 5 mg, 1 × 25 mg) (am) 2 capsules (1 × 5 mg, 1 × 25 mg) (pm)	2 capsules (2 × 0 mg) (am) 2 capsules (2 × 0 mg) (pm)

Abbreviations: am = morning; bid = twice daily; MAD = multiple ascending dose; pm = afternoon/evening

¹ Dose levels will be based on data from Part A and emerging PK data.

² An equivalent number of capsules will be administered to subjects receiving placebo.

³ Dose to be administered twice daily, 8 hours apart (refer also to [Section 5.3.3](#)).

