6.20.2. Maximum Tolerated Dose Definition

The maximum tolerated dose (MTD) is defined as the dose below a non-tolerated dose and therefore can only be determined by the observation of a dose level, which is no longer considered acceptable in healthy subjects.

In this study, a dose will be considered non-tolerated and dose escalation will cease if 2 or more subjects in a cohort experience an AE of Grade 3 or higher occurring within 48 hours of administration of KNX100 or placebo at the dose level. Once the non-tolerated dose is defined,

the MTD will be confirmed at the previous dose level below the non-tolerated dose, or a dose between the non-tolerated dose and the last tolerated dose may be investigated. If the dose-escalation scheme is successfully completed for all escalating doses, 35 mg/day will be the highest dose studied (refer to [Section 5.3.2](#) and [Section 5.3.3](#) for the dosing schedule).

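### Protocol 6.20.2 names 35 mg/day as the highest dose studied, but the schedules it cites plan 50 mg in Part A and 60 mg/day in Part B Cohort 3

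*Protocol*

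**What the plan says.** The protocol states a maximum or planned top dose in milligrams in several places.

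- **Section 3.2.2:** "An upper limit of 35 mg per day is supported by the nonclinical data and human PK data". The limit is tied to one tenth of the exposure at the no-effect level in the 14-day dog EEG study, and the sentence adds that emerging safety and PK data will guide it.
- **Section 6.20.2:** if every planned escalation is carried through, "35 mg/day will be the highest dose studied". The cross-reference is to both 5.3.2 (Part A) and 5.3.3 (Part B).
- **Synopsis:** Part A rises to at most 50 mg. Part B starts at 10 mg, "increasing up to 35 mg per dose, as tolerated".
- **Section 3.2:** for Part A Cohorts 2 to 4, "the KNX100 dose will be increased as agreed by the CRC up to a maximum of 50 mg of KNX100", or to the exposure cap if that is reached sooner.
- **Section 5.2:** "Part A will evaluate doses of KNX100 starting with 5 mg and increasing up to a maximum of 50 mg per day".
- **Section 5.3.2, Table 3:** Part A Cohort 4 is 50 mg, given as two 25 mg capsules.
- **Section 5.3.3, Table 4:** Part B Cohort 3 is entered as 30 (bid) in a column headed mg/day. One 5 mg and one 25 mg capsule are listed for the morning and the same again for the afternoon or evening, with the footnote "Dose to be administered twice daily, 8 hours apart". The text of this section gives no upper figure in mg; it says that dose strengths from 10 mg "up to the clinical exposure cap will be selected based on the tolerability and pharmacokinetics of the previous dose".

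A separate exposure cap for KNX100 and KNX100A appears in Sections 3.2.2, 5.3.4 and 6.20.1. The SAP gives no ceiling in mg, so it does not settle the matter.

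**The concern.** This is a first-in-human study, and Section 3.2.1 makes CNS effects, with convulsions in animals, the main basis for choosing the dose regimens. A stated highest dose is what an ethics committee reads, what the site checks and what the Cohort Review Committee (CRC) escalates towards. If Part A Cohort 4 or Part B Cohort 3 is dosed as tabulated, the schedule is followed and the limit in 6.20.2 is exceeded. If 6.20.2 is followed, those two of the seven planned cohorts cannot be given as planned. For the twice-daily cohort it is also unclear whether the limit applies to each dose or to the day, and the two differ by a factor of two.

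**Working it through.** No modelling is needed: the check converts each planned cohort to mg per day and compares it with the stated 35 mg/day.

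Formula: daily dose = (sum of capsule strengths per administration) × (administrations per day). Doses and capsules are from Tables 3 and 4.

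| Cohort | Per administration | Per day | Per day ÷ 35 |
|---|---|---|---|
| Part A, 1 | 1 × 5 = 5 mg | 5 mg | 0.14 |
| Part A, 2 | 3 × 5 = 15 mg | 15 mg | 0.43 |
| Part A, 3 | 1 × 25 = 25 mg | 25 mg | 0.71 |
| Part A, 4 | 2 × 25 = 50 mg | 50 mg | **1.43** |
| Part B, 1 | 2 × 5 = 10 mg | 10 mg | 0.29 |
| Part B, 2 | 5 + 25 = 30 mg | 30 mg | 0.86 |
| Part B, 3 | 5 + 25 = 30 mg | 2 × 30 = 60 mg | **1.71** |

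Five cohorts fit under 35 mg/day and two do not. The Table 4 entry for Cohort 3 is a per-dose figure under a per-day heading; the capsule counts establish 60 mg/day.

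Next, can some reading of the 35 mg limit make the text agree?

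1. **As written (per day, both parts).** Both conflicts stand: 50 against 35 and 60 against 35.
2. **Per day, Part B only.** The Part A conflict goes, but 60 mg/day against 35 mg/day remains. Section 6.20.2 also cites the Part A schedule, which tells against this reading.
3. **Per dose, both parts.** Cohort 3 of Part B fits (30 mg is below 35 mg), but the single 50 mg dose in Part A does not. Sections 3.2.2 and 6.20.2 both say per day.
4. **Per dose, Part B only.** Nothing in the tables conflicts, and this matches the synopsis. But it changes both the unit and the scope of the statement in 6.20.2.

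So no reading that keeps the wording of 6.20.2 agrees with the schedules it cites. That the fourth reading is consistent does not show that it is the intended or correct one.

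**The case against.** The best defence is that dosing is really governed by exposure. Section 3.2 stops Part A at 50 mg or at the cap, whichever comes sooner. Section 3.2.2 stops escalation not only when Cmax or AUC passes the cap but also when it is expected to. Section 6.20.1 says the cap will not be exceeded, and Section 3.2 has the Cohort 3 dose chosen from PK in the preceding cohort. Footnotes to both tables make the doses provisional. Section 3.2.2 is itself a qualified statement, which could sit beside 50 mg as an outer bound. The Part A maximum is also consistent in four places (synopsis, 3.2, 5.2 and Table 3), and per dose against per day matters only for the one twice-daily cohort.

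All of this stands, and it limits the practical risk. It does not rescue 6.20.2, which describes what happens when the full schedule is completed and names a figure that the completed schedule exceeds. A second limit, even a binding one, does not reconcile the first.

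Some stronger readings are tempting but not supported:

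- **That 70 mg/day is planned.** Two doses at the synopsis limit would give 2 × 35 = 70 mg/day, but no table plans this.
- **That 35 mg is wrongly derived.** Section 3.2.1's formula with its CL/F of 356,000 mL/h puts the AUC cap of 82.7 h×ng/mL at 356,000 × 82.7 / 1,000,000 = 29.4 mg. But scaling Cmax linearly from that section's 20 mg for 46 ng/mL gives 20 × 84.9 / 46 = 36.9 mg, which is compatible with 35 mg. The protocol shows no derivation, so no error is demonstrated.
- **That 30 mg twice daily is predicted to break the AUC cap.** This depends on the interval compared. For Cohort 3 the SAP (6.3.1, MAD table) lists a whole-profile AUC as well as 0–8 h and 8–16 h AUCs. Sampling ends at 16 h in one footnote of protocol Appendix 3, while another footnote and Sections 5.3.4 and 9.8.1 refer to 24-hour data. No firm prediction follows.

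**Conclusion.** The point holds as an internal inconsistency in a stated safety limit, not as an arithmetic error. Against the 35 mg/day named in 6.20.2, the schedules it cites plan 1.43 times as much in Part A Cohort 4 and 1.71 times as much in Part B Cohort 3. The synopsis adds a different unit for Part B. These ratios rest only on the protocol's own doses and capsule counts; no PK assumption enters.

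A reader might infer that dosing is unbounded, or that subjects would certainly receive more than the sponsor considers safe. The documents do not support either: the exposure cap applies, Section 6.20 suspends dosing on epileptiform EEG findings, and the CRC can alter the planned doses. The defect is that the written limits disagree, and in a first-in-human protocol that has to be corrected.

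**What to change.** Amend the protocol so that the synopsis, Sections 3.2.2 and 6.20.2, and Table 4 in Section 5.3.3 agree with Sections 3.2 and 5.2 and Table 3 in Section 5.3.2. Each part should carry one ceiling in mg, stated as per dose or per day, and 6.20.2 should say which part it covers and match the schedules it cites. The Cohort 3 entry in Table 4 should agree with its column heading. Which figures should stand is a decision for the sponsor's clinical team; this review takes no view.

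The cost is amendment wording and its review, with no extra subjects, visits or samples.

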3.3. Study Duration and Dates

This study is expected to run for approximately 12 months from the start of subject screening to the last subject finishing the study.

4. STUDY POPULATION SELECTION

4.1. Study Population

This study will enroll approximately 64 healthy volunteers at a single site in Australia.

This clinical study can fulfill its objectives only if appropriate subjects are enrolled. The following eligibility criteria are designed to select healthy subjects for whom protocol treatment and procedures are considered appropriate. All relevant medical and non-medical conditions should be taken into consideration when deciding whether this protocol is suitable for a particular subject.

4.2. Inclusion Criteria

Subjects will be eligible for participation in the study only if they meet ALL of the following inclusion criteria.

None of the inclusion criteria are eligible for re-screening. No waivers will be granted and any deviation from below will be recorded as a major protocol deviation. An exception can apply for subjects who meet the inclusion and exclusion criteria, but then miss a cohort because it is filled. This would mean they are no longer eligible due to the 28-day screening window lapse. These are the only subjects that may be rescreened.

1. Ability to understand and provide written informed consent.
2. Body mass index (BMI) within the range of 18-32 (inclusive).
3. Healthy male and female volunteers ≥ 18 and ≤ 55 years old at Screening.
4. Able and willing to comply with the requirements of the study and complete the full sequence of protocol related doses, procedures, and evaluations.
5. Willing to agree not to use alcohol or recreational drugs and willing to have drug screening, prior to the first dose of KNX100 and if drug use is suspected while active in the study.
6. Willing to agree not to smoke cigarettes or use tobacco-based products prior to the first dose of KNX100 and for the entire duration of the study.

7. Males who are sexually active must use a condom OR be abstinent OR have the same sex partner OR be surgically sterile OR have partner who is of non-childbearing potential, for at least 90 days after the last dose of investigational drug. If female partner is a Woman of Child-Bearing Potential (WOCBP), the female partner must use highly effective methods of contraception, defined as below:
 - Hormonal methods of contraception including oral contraceptives containing combined estrogen and progesterone, a vaginal ring, injectable and implantable hormonal contraceptives, intrauterine hormone-releasing system (e.g., Mirena) and progestogen-only hormonal contraception associated with inhibition of ovulation.
 - Nonhormonal intrauterine device,
 - Bilateral tubal occlusion.

Refer to [Section 6.9](#) for further detail on contraception.

4.3. Exclusion Criteria

Subjects will **not** be eligible for participation in the study if they meet ANY of the following exclusion criteria.

1. Clinically significant history or presence of significant cardiovascular, respiratory, hepatic, renal, gastrointestinal, endocrinological, hematological, neurological, or psychiatric disorder. Any surgical or medical history which may significantly alter the absorption, metabolism, or elimination of drugs or constitute a risk when taking the study intervention; or interfering with the interpretation of data (e.g., gastric bypass, cyclical vomiting, etc.). This includes a history of lymphoma, leukemia, or any malignancy within 5 years except for basal cell or squamous epithelial carcinomas of the skin that have been resected with no evidence of metastatic disease for 3 years.
2. Subjects who have a sitting or semi-supine blood pressure at screening or Day-1, after resting for at least 3 minutes of systolic blood pressure >140 or <100 mmHg, or diastolic blood pressure >90 or <60 mmHg.
3. Subjects who have a sitting or semi-supine pulse rate at screening or Day-1, after resting for at least 3 minutes, outside the range of <50 or >90 beats/minute
4. Subjects who donated blood or who had a comparable blood loss (approximately 500 mL) during the last 30 days prior to start of this study and while on study.
5. Clinically significant findings on the screening, Day -1, or predose Day 1 electrocardiogram (ECG) or physical examination, including QTcF duration >450 ms for males and >470 ms for females on ECG.
6. Thyroid function tests outside the normal reference ranges and deemed clinically significant by the study PI (and upon repeat).

7. Safety laboratory tests that are outside the normal reference ranges and deemed clinically significant by the study PI (and upon repeat).
8. Any history of meningitis, septicemia, or pneumonia.
9. Any history or family history (first or second degree relative) of seizure disorder, febrile convulsions.
10. Any clinically significant medical history of closed head trauma.
11. Any history of anaphylaxis or other significant allergy.
12. Any current diagnosis or clinically significant medical history of psychiatric illness as diagnosed and documented by a medical practitioner and as defined by the American Psychiatric Association Diagnostic and statistical manual of mental disorders 5th edition (DSM-5).
13. Subjects with a history of chronic alcohol (regular daily intake of more than three standard drinks) or drug abuse within the last 6 months prior to first administration, or evidence of such abuse as indicated by the laboratory profile conducted during the screening examination.
14. Subjects who have received prescription drugs or over-the-counter (OTC) medication including dietary supplements, COVID-19 vaccine, standard dose vitamins, or herbal products within 14 days prior to the first administration (with the exception of the oral contraceptive pill).
15. Subjects who received any treatment agents known to alter the major organs or systems within 30 days prior to the first administration (e.g., diuretics, nephro- or liver toxic medication, barbiturates, phenothiazines, cimetidine, more than 1.0 L of caffeine-containing beverages per day, etc.).
16. Diagnosed infection of any kind, e.g., viral, bacterial, fungal, or mycobacterial within 1 month prior to the first dose of KNX100 or current fever or clinical signs or symptoms of infection at screening or Day -1.
17. Treatment with an unapproved investigational therapeutic agent within 30 days (or 5-half-lives for small molecule agents) prior to the first dose of KNX100.
18. Females who are pregnant (positive pregnancy test at screening or prior to first dose), lactating or unable/unwilling to use defined methods of contraception throughout the study.

Laboratory assessments conducted at screening for any exclusion criterion may be repeated once to rule out a laboratory error. Only the value leading to inclusion of the subject will be recorded. Vital signs recorded outside the exclusion criteria ranges may also be repeated once for confirmation.

